## **Evaluation of Target Lesions**

Complete Response	Disappearance of all target lesions. Any pathological lymph nodes (whether target or non-target) must have reduction in short axis to < 10 mm.
Partial Response	At least a 30% decrease in the sum of the LD of target lesions, taking as reference the baseline sum LD.
Stable Disease	Neither sufficient shrinkage to qualify for partial response nor sufficient increase to qualify for PD, taking as reference the smallest sum LD since the treatment started.
Progressive Disease	At least a 20% increase in the sum of the LD of target lesions, taking as reference the smallest sum on study (this includes the baseline sum if that is the smallest on study). In addition to the relative increase of 20%, the sum must also demonstrate an absolute increase of at least 5 mm. The appearance of one or more new lesions is also considered progression.

# **Evaluation of Non-target Lesions**

Complete Response	Disappearance of all non-target lesions and normalization of tumor marker level.
Stable Disease/Incomplete Response	Persistence of one or more non-target lesion(s) or/and maintenance of tumor marker level above the normal limits.
Progressive Disease	Appearance of one or more new lesions and/or unequivocal progression of existing non-target lesions.

If tumor markers are initially above the institutional ULN, they must normalize for a patient to be considered a complete *responder*.

### **Evaluation of Best Overall Response**

The best overall response is the best response recorded from the start of the treatment until disease progression/recurrence (taking as reference for PD the smallest measurements recorded since the treatment started). The patient's best response assignment will depend on the achievement of both measurement and confirmation criteria.

### Time Point Response

A response assessment will occur at the protocol-specified time points. The tables below provide a summary of the overall response status calculation at each time point for patients who have measureable and non-measureable disease (non-target disease only).

Time Point Response: Patients with Target (+/- Non-target) Disease			
Target Lesions	Non-target Lesions	New Lesions	Overall Response
CR	CR	No	CR
CR	Non-CR/non-PD	No	PR
CR	Not evaluated	No	PR
PR	Non-PD or not evaluated	No	PR
SD	Non-PD or not evaluated	No	SD
Not Evaluated	Non-PD	No	NE
PD	Any	Yes or No	PD
Any	PD	Yes or No	PD
Any	Any	Yes	PD

NE = Not evaluable

Evaluation of Best Overall Response when Confirmation of CR and PR Required			
Overall Response	Overall Response	Best Overall Response	
First Time Point	Subsequent Time Point		
CR	CR	CR	
CR	PR	SD, PD or PR a	
CR	SD	SD provided minimum criteria for SD duration met, otherwise, PD	
CR	PD	SD provided minimum criteria for SD duration met, otherwise, PD	
CR	NE	SD provided minimum criteria for SD duration met, otherwise, NE	
PR	CR	PR	
PR	PR	PR	
PR	SD	SD	
PR	PD	SD provided minimum criteria for SD duration met, otherwise, PD	
PR	NE	SD provided minimum criteria for SD duration met, otherwise, NE	
NE	NE	NE	

If a CR is truly met at first time point, then any disease seen at a subsequent time point, even disease meeting PR criteria relative to baseline, makes this disease PD at that point (since disease must have reappeared after CR). Best response would depend on whether minimum duration for SD was met. However sometimes 'CR' may be claimed when subsequent scans suggest small lesions were likely still present and in fact the patient had PR, not CR at the first time point. Under these circumstances, the original CR should be changed to PR and the best response is PR.

### Missing Assessments and Not Evaluable Designation

When no imaging/measurement is done at all at a particular time point, the patient is not evaluable (NE) at that time point. If only a subset of lesion measurements are made at an

assessment, usually the case is also considered NE at that time point, unless a convincing argument can be made that the contribution of the individual missing lesion(s) would not change the assigned time point response, which is most likely to occur in the case of PD; e.g., if only 2 of 3 baseline target lesions are assessed and result in a > 20% increase in the sum, then the patient would be assessed as a PD regardless of the missing lesion.

Patients with a global deterioration of health status requiring discontinuation of treatment without objective evidence of disease progression at that time should be classified as having symptomatic deterioration. Every effort should be made to document the objective progression, even after discontinuation of treatment.

In some circumstances, it may be difficult to distinguish residual disease from normal tissue. When the evaluation of CR depends on this determination, it is recommended that the residual lesion be investigated (FNA/biopsy) prior to confirming the complete response status.

## **Confirmatory Measurement/Duration of Response**

### Confirmation

CT scans are required every  $8\pm 1$  weeks. If an initial CR or PR is noted, confirmatory scans must be performed  $4\pm 1$  week later. In the case of SD, follow-up measurements must have met the SD criteria at least once after study entry at a minimum interval of no less than  $4\pm 1$  weeks.

# **Duration of Overall Response**

The duration of overall response is measured from the time measurement criteria are met for CR or PR (whichever is first recorded) until the first date that recurrent or PD is objectively documented (taking as reference for PD the smallest measurements recorded since the treatment started).

The duration of overall CR is measured from the time measurement criteria are first met for CR until the first date that recurrent disease is objectively documented.

### **Duration of Stable Disease**

SD is measured from the start of the treatment until the criteria for progression are met, taking as reference the smallest measurements recorded since the treatment started.

# Appendix B

# Eastern Cooperative Oncology Group Performance Status Scale

ECOG I	ECOG Performance Status		
0	Fully active, able to carry on all predisease performance without restriction.		
1	Restricted in physically strenuous activity but ambulatory and able to carry out work of a light or sedentary nature (e.g., light house work or office work).		
2	Ambulatory and capable of all self care but unable to carry out any work activities. Up and about more than 50% of waking hours.		
3	Capable of only limited self care; confined to bed or chair more than 50% of waking hours.		
4	Completely disabled. Cannot carry on any self care. Totally confined to bed or chair.		
5	Dead.		

# Appendix C

# Inhibitors and Inducers of CYP2C8, CYP2D6 and P-gp

The following list of inhibitors and inducers of CYP2C8, CYP2D6 and P-gp are to be avoided or used with caution in patients receiving CO-1686. Selection of an alternative concomitant medication with no or minimal enzyme inhibition or induction potential is recommended.

## Inhibitors and Inducers of CYP2C8 and CYP2D6

CYP Enzyme	Inhibitors	Inducers
	(Avoid)	(Caution)
CYP2C8	gemfibrozil trimethoprim glitazones montelukast quercetin	rifampin
CYP2D6	bupropion fluoxetine paroxetine quinidine	

# Inhibitors and Inducers of P-gp

Enzyme	Inhibitor	Inducer
	(Caution)	(Caution)
P-gp	amiodarone	avasimibe
	azithromycin	carbamazepine
	captopril	phenytoin
	carvedilol	rifampin
	clarithromycin	St. John's wort
	conivaptan	tipranavir/ritonavir
	cyclosporine	
	diltiazem	
	dronedarone	
	erythromycin	
	felodipine	
	itraconazole	
	ketoconazole	
	lopinavir	
	ritonavir	
	quercetin	
	quinidine	
	ranolazine	
	verapamil	

### Appendix D

Study CO-1686-022 Extension Phase

### **OBJECTIVE OF THE EXTENSION PHASE**

The purpose of the Extension Phase is to allow patients to continue on study but to avoid unnecessary collection of data that will no longer be analyzed or required for regulatory purposes, whilst maintaining an appropriate level of safety monitoring.

An important change of the Extension phase is the removal of the option for patients to crossover to CO-1686 following radiographic progression on erlotinib. The decision to remove the crossover option to CO-1686 was based on the recommendation of the DMC, which oversees the risk/benefit aspects of the study. Patients and their physicians are directed to seek alternative treatments, which can fulfill this need.

In addition, this amendment also introduces the availability of NAT2 testing for patients, an indirect indicator of the likelihood of developing hyperglycaemia and QTc prolongation. The availability and disclosure of this information to the patients's treating physician will not affect the monitoring and associated treatment guidelines for these adverse events.

### Additional information on efficacy/safety aspects

The most current clinical and non-clinical updates, in particular those pertaining to efficacy and safety data, are provided in the current Investigator's Brochure, in which integrated summaries of efficacy and safety data are presented.

### Additional information relating to hyperglycemia and QTc prolongation

The polymorphic enzyme NAT2 mediates the N-acetylation of M502 to form M544 and also plays a role in the elimination of M460. NAT2 genotype polymorphism was assessed for the group of patients who received CO-1686 at 500 mg BID, 625 mg BID, 750 mg BID, and 1000 mg BID and who gave additional informed consent for genomic testing. The NAT2 genotype polymorphism testing was performed using an assay based on polymerase chain reaction (PCR) followed by mass spectrometry to identify single nucleotide polymorphisms in NAT2. Based on NAT2 genotype results, patients were classified as having "low", "intermediate", and "rapid" acetylator phenotype. Acetylator status is currently available for 635 patients. Additional testing will be completed as additional samples are received.

Adverse event and laboratory data based on NAT2 phenotype are summarized in Appendix D, Table 1, Appendix D, Table 2, and Appendix D, Table 3. Analyses are presented by acetylator status for all doses combined, since the combined-dose findings were consistent with the findings within each dose group.

Appendix D, Table 1 demonstrates that Grade 3 events are less common in patients who are classified as "rapid" acetylators. As expected, the relationship is most clear for hyperglycemia and QT-prolongation, while other adverse events of special interest (AESIs) appear to be less closely associated with acetylator status. Appendix D, Table 2 shows that hyperglycemia appears to be less frequent and less severe in rapid acetylators. Appendix D, Table 3 shows that QTcF prolongation on ECG appears to be less frequent and less severe in rapid acetylators.

# Appendix D, Table 1.

**Grade 3 or Greater Treatment-emergent Adverse Events by Acetylator Status** 

	Overall (N = 635)			
	Slow (n=300)	Intermediate (n=259)	Rapid (n=76)	
Overall	243 (81%)	194 (75%)	48 (63%)	
Hyperglycemia (CT)	131 (44%)	66 (26%)	13 (17%)	
QTc prolongation (CT)	44 (15%)	19 (7%)	1 (1%)	
Malignant neoplasm progression	39 (13%)	39 (15%)	8 (11%)	
Cataracts (CT)	12 (4%)	9 (4%)	7 (9%)	
Pneumonitis (CT)	3 (1%)	4 (2%)	0	
Diarrhea	13 (4%)	16 (6%)	1 (1%)	

**Abbreviation:** CT=combined terms.

Appendix D, Table 2. Hyperglycemia Lab-shift by Acetylator Status

	Overall (N = 635)		
			Rapid (n = 76)
Subjects with any post-baseline glucose values > 250 mg/dL	121 (40%)	65 (25%)	17 (22%)
Subjects with 2 or more post- baseline glucose values > 250 mg/dL	51 (17%)	36 (14%)	7 (9%)
Subjects with any post-baseline glucose values > 500 mg/dL	11 (4%)	7 (3%)	1 (1%)
Subjects with 2 or more post- baseline glucose values > 500 mg/dL	3 (1%)	0 (0.0)	0 (0.0)

Appendix D, Table 3. QTcF Changes on ECG by Acetylator Status

	Overall (N = 635)		
	Slow (n = 300)	Intermediate (n = 259)	Rapid (n = 76)
QTcF Post-baseline ≥ 450 msec	198 (66%)	131 (51%)	34 (45%)
QTcF Post-baseline ≥ 481 msec	92 (31%)	44 (17%)	7 (9%)
QTcF Post-baseline ≥ 501 msec	59 (20%)	22 (9%)	1 (1%)
Two of more within 3 days ≥ 501 msec	19 (6%)	10 (4%)	0 (0.0)
QTcF Change from Baseline > 30 msec	246 (82%)	171 (66%)	47 (62%)
QTcF Change from Baseline > 60 msec	141 (47%)	57 (22%)	9 (12%)

**Abbreviation:** ECG=electrocardiogram.

For those patients ongoing on CO-1686 trials, informed consent and testing for NAT2 polymorphism status will be offered and the results will be shared with the treating physician. It will be up to the patient in consultation with the treating physician to decide continued participation in the trial in light of the acetylator status results or whether alternative treatment options should be sought.

Regardless of acetylator status, monitoring should be the same for all patients receiving CO-1686 whilst on treatment.

### STUDY DESIGN

## **Treatment Regimen and Duration of Therapy**

The option to crossover to CO-1686 following radiographic progression on erlotinib will no longer be available to patients in this Extension Phase (see Objective of the Extension Phase).

All patients will sign an informed consent which explains the rationale for closing the CO-1686 clinical development program for NSCLC and the option for ongoing patients to continue receiving study treatment, should they decide to do so and/or if in the opinion of their treating physician they continue to receive clinical benefit. However, the

suitability of alternative treatment options should be considered by the treating physician and discussed with the patient prior to taking the decision to continue treatment with CO-1686 CO-1686 will be administered daily on a 28-day cycle. Dosing will be delayed or decreased according to protocol-specified toxicity criteria (Section 7.4). Each dose should continue to be taken with 8 oz. (240 mL) of water and with a meal or within 30 minutes after a meal two times per day. Tablets should be swallowed whole.

Treatment may continue until disease progression or intolerable toxicity. Please note, patients on CO-1686 or erlotinib, may opt to continue to receive treatment with CO-1686 following radiographic progression as outlined in the NCCN guidelines for treatment of NSCLC with EGFR TKIs if patient provides additional consent, the investigator feels it is in the patient's best interest and with sponsor approval. It is important that before deciding to continue treatment with CO-1686 or erlotinib post progression, in either of the two stated scenarios, additional treatment options are explored and discussed with the patient by the treating physician. In general, eligible patients may include those with asymptomatic systemic progression or locally symptomatic progression, such as brain metastases amenable to local treatment, with concomitant asymptomatic systemic progression or continued systemic disease control. This must be discussed with the sponsor and will be reviewed on a case-bycase basis.

If a patient continues treatment post-progression, all Extension Phase study assessments should continue per protocol and data should be captured in the eCRF. The patient should be discontinued from treatment once it is clear that no further clinical benefit can be achieved.

Both the hyperglycemia and QTc management guidelines (Section 7.4) should be followed during this extension phase and any modifications/deviations from these guidances should be discussed and agreed upon with the sponsor prior to implementation.

Once study treatment has been discontinued and the End of Treatment visit has been completed, study participation will cease. Investigational centers will interpret tumor scans locally for the purpose of making treatment decisions and for final tumor response evaluation. The study will close once all patients have either completed participation, have transferred to a locally approved treatment access program (e.g. a named patient program) in accordance with relevant local regulations or the sponsor decides to close the study.

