concomitant asymptomatic systemic progression or continued systemic disease control. Patients randomized to the erlotinib arm may also continue to be treated post-progression with erlotinib if this agent is to be continued as a single agent. Palliative radiation therapy intended to provide relief of cancer-related symptoms is permitted while the patient is on study, as long as there is no evidence of disease progression per RECIST Version 1.1. Such palliative radiotherapy must be approved prospectively by the sponsor and documented in the electronic case report form (eCRF). If the erlotinib dose is to be escalated or other agents are to be added in, the patient must be discontinued from the study, perform End-of-Treatment Visit procedures, and continue to the follow-up portion of the study. Any patient on this study who is to be treated post-progression must be discussed with the sponsor, and will be reviewed on a case-by-case basis. If a patient continues treatment with CO-1686 or erlotinib post-progression, all study assessments including efficacy assessments, safety assessments, QOL administration, and blood collection for biomarker analysis and exploratory research should continue per protocol. The patient should be discontinued from treatment once it is clear that no further clinical benefit can be achieved.

In the Phase 2 part only, for patients initially randomized to erlotinib, there is an optional crossover phase following disease progression per RECIST Version 1.1 and confirmation of T790M+ disease by local laboratory using tissue sample collected after disease progression. Patients who progress on erlotinib who have not developed the T790M mutation are not eligible to receive CO-1686 in the crossover part of the study, because for these patients, progression on erlotinib is likely driven by other mechanisms that are unlikely to respond to CO-1686. Patients in the crossover phase will continue all study assessments including efficacy assessments, safety assessments, QOL administration, and blood collection for biomarker analysis and exploratory research as outlined in Section 9.3.

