## 9 STUDY PROCEDURES

Table 9-1 summarizes the procedures and assessments to be performed for all patients.

Table 9-2 summarizes the procedures and assessments to be performed in Phase 2 only for patients randomized to erlotinib, who progress on study, demonstrate T790M+ status at the screening biopsy, and agree to participate in the crossover component of the study to receive PO CO-1686 treatment.

All procedures and assessments are to be completed within  $\pm 1$  day of the scheduled time point and are synchronized with C1D1 of CO-1686 or erlotinib treatment unless otherwise noted.

With the introduction and following approval of this protocol amendment 3 version, crossover to CO-1686 after progression on erlotinib is no longer an option. All ongoing patients, will be treated on the Extension Phase of the study and should follow the schedule of assessments provided in Appendix D.

Table 9-1: Schedule of Assessments in Phase 2 (Before Crossover) and in Phase 3

	Scre	ening			7	Treatment Po		T			Follow-up (Every 8 ± 1 weeks for
Procedure b	≤35 Days Prior to Cycle 1 Day 1	≤ 14 Days Prior to Cycle 1 Day 1	Cycle 1 Day 1 (C1D1) c	Cycle 1 Day 4 ± 1 Day d	Cycle 1 Day 8 ± 1 Day d	Cycle 1 Day 15 ± 1 Day d	Cycle 2 Day 1 (28 ± 3 days after C1D1)	Cycle 2 Day 15 ± 1 Day d	Cycle 3+ Every 28 ± 3 Days	End-of- Treatment t 28 Days ±7 Days After Last Dose	scans, every 3 months ± 7 days for survival and subsequent therapy starting at End-of- Treatment)
Informed consent	X										
Medical/oncology history	X										
Physical examination		X	X				X		X	X	
ECOG performance status		X	X				X		X	X	
Vital signs e , height (screening only) and weight		X	X				X		X	X	
Prior/concomitant medications and procedures f	X		X				X		X	X	
Contraceptive counseling g	X									X	
Serum pregnancy test h		X								X	
Hematology, including reticulocytes i		X	X				X		X	X	
Fasting serum chemistry j		X	X	Fasting glucose only	Fasting glucose only	Fasting glucose only	X	Fasting glucose only	X	X	
Urinalysis k		X									

Table 9-1: Schedule of Assessments in Phase 2 (Before Crossover) and in Phase 3 (Cont.)

	Scre	ening				Treatment P					Follow-up (Every 8 ± 1 weeks for

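### Appendix D names patients on both drugs but only CO-1686 as the drug continued after progression, so it either conflicts with the removal of crossover or omits erlotinib

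*Combined protocol and SAP*

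**What the plan says.** Appendix D, Treatment Regimen and Duration of Therapy, opens with the removal of crossover: "The option to crossover to CO-1686 following radiographic progression on erlotinib will no longer be available to patients in this Extension Phase". It refers back to the Objective of the Extension Phase, which gives the basis: the decision "was based on the recommendation of the DMC, which oversees the risk/benefit aspects of the study". The opening of Section 9 repeats that "crossover to CO-1686 after progression on erlotinib is no longer an option". The Synopsis, Section 3 and Section 5.1.5 say the same.

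Later in the Treatment Regimen section comes the post-progression permission: "patients on CO-1686 or erlotinib, may opt to continue to receive treatment with CO-1686 following radiographic progression", "if patient provides additional consent, the investigator feels it is in the patient's best interest and with sponsor approval". The next sentence requires other options to be explored and discussed "before deciding to continue treatment with CO-1686 or erlotinib post progression, in either of the two stated scenarios". The section then describes the patients generally considered eligible, and calls for discussion with the sponsor and case-by-case review.

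Elsewhere the continued drug is stated differently. The Study Design part of the Synopsis gives either CO-1686 or erlotinib as the drug a patient may continue after radiographic progression. Section 5.1.2 first gives the permission for CO-1686 and then adds: "Patients randomized to the erlotinib arm may also continue to be treated post-progression with erlotinib", on condition that it remains a single agent.

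**The concern.** This section governs treatment for every patient still on study, and a site would turn to it when a patient progresses. It removes a route from erlotinib to CO-1686 and then, further down, contains a sentence that can be read as opening one. A site, a patient or a sponsor reviewer could reach different conclusions about which drug may be requested for an erlotinib patient.

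What is at stake is which drug a patient may be given after progression, on a point where the protocol says that it acted on the DMC's recommendation. That makes the conflict more than editorial, although it sits in a single sentence.

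**Working it through.** The plan gives no figure to reproduce here; the check is a comparison of texts.

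**1. Who and which drug.** The sentence applies to patients on CO-1686 or erlotinib, the action is to continue, and the drug is CO-1686. For a patient on CO-1686 this is coherent. For a patient on erlotinib there is no CO-1686 treatment to continue. Appendix D, Eligibility and Number of Patients, confirms that the Extension Phase covers patients on either drug, so the second group is not empty by definition.

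**2. Reading A: an erlotinib patient may receive CO-1686 after progression.** The pairing of patients and drug supports it. The opening of the same section, the Objective of the Extension Phase and Section 9 contradict it.

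**3. Reading B: erlotinib was left out as the drug that erlotinib patients may continue.** The word for continuing supports it. So do the next sentence, which names both drugs, the Synopsis and Section 5.1.2. The sentence itself does not say it, and the two scenarios mentioned in the next sentence are not set out anywhere.

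**4. Does the rest of Appendix D settle it?** No.
- The Withdrawal Criteria permit post-progression treatment without naming a drug.
- The dosing text in the same section, the dispensing row of Table 4 and the dispensing item under Day 1 of Each Cycle name only CO-1686, although Table 4 is headed as applying to all patients.
- Table 4 has no crossover assessments and no biopsy. This favours Reading B, but only by inference.

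**5. What Reading A would mean beside the former crossover.**

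| Item | Former crossover (Synopsis; Section 9.3; Table 9-2) | Appendix D sentence, Reading A |
|---|---|---|
| Study part | Phase 2 only | No limit stated |
| T790M after progression | Required | Not stated |
| Laboratory criteria (Inclusion Criterion 8) | Required | Not stated |
| QT-prolonging drugs and cardiac abnormalities (Exclusion Criteria 7 and 9) | Exclude | Not stated |
| Sponsor approval | Required | Required |
| ECGs early in the first CO-1686 cycle | Days 8 and 15 | None scheduled; Day 1 of each cycle |

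On ECGs, Appendix D keeps the patient's existing cycle count. After Cycle 12, patients whose QT stayed below 470 ms may move to every third cycle. With 28-day cycles that is 3 × 28 = 84 days between scheduled ECGs. Section 3.2.1 places the onset of QTc increase between Day 1 and Day 15. The QTc and hyperglycemia guidance in Section 7.4 does carry over, including its list of fasting glucose visits, so this gap concerns ECG visits and entry conditions, not all monitoring.

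Taken literally, the sentence would therefore be wider than the route that was removed, with a schedule not built for a patient newly starting CO-1686. The same facts also suggest that no such route was intended. They do not remove the conflict in the words.

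**The case against.** The strongest answer is that this is a drafting slip which few readers would act on. The sentence speaks of continuing, and an erlotinib patient cannot continue CO-1686. The removal of crossover is explicit, is repeated in several places and comes first in the section. The next sentence and the parallel passages name both drugs. Each request also needs additional consent, the investigator's judgement, a discussion of alternatives, sponsor approval and case-by-case review, and the sponsor is the party that removed crossover.

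Most of this stands. Reading B is the more likely intention, and the chance of unintended exposure is reduced. But it remains an inference: on Reading B the sentence still omits the drug that erlotinib patients may continue, and the dispensing text does not supply it. Both readings call for a correction.

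Three stronger readings are tempting and are not supported.
- A reader might infer that the amendment reinstates crossover. The repeated removal and the word for continuing speak against that; the text is contradictory, not permissive.
- A reader might infer damage to the efficacy or survival analyses. The primary endpoint ends at first progression or death (Section 11.2.4.1), so post-progression treatment cannot alter it. In the Extension Phase, participation ends after the End of Treatment visit, Table 4 has no row for survival status or subsequent therapy, and the stated aim is to stop collecting data that will not be analyzed. The Synopsis already warns that control-arm crossover may limit the OS data.
- A reader might infer what the DMC concluded about CO-1686 after erlotinib. The documents say that the DMC recommended the removal and that it oversees risk and benefit; they do not give its reasons.

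**Conclusion.** Wrong as written: an internal contradiction in current operative text, not a disputed design choice. The post-progression sentence either conflicts with the removal of crossover or fails to name the drug that erlotinib patients may continue, and Appendix D does not settle which.

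The size is one sentence, bearing on any ongoing erlotinib patient who reaches radiographic progression. That number is not in the documents and no estimate is offered. No planned analysis is shown to be affected.

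The conclusion rests on the wording alone. It does not assume that any patient was treated under the literal reading, or that the sponsor would approve such a request. It should be corrected because the section governs which drug a patient may be given, and the literal wording carries none of the T790M, cardiac or QT entry conditions of the former route.

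**What to change.** Reconcile the sentence in Appendix D, Treatment Regimen and Duration of Therapy, with the opening of that section, the Objective of the Extension Phase, the opening of Section 9, the Study Design part of the Synopsis and Section 5.1.2. The drug that each arm may continue after progression should then be stated once and consistently. Which clinical rule should stand is for the sponsor and its clinical advisers; none is proposed here.

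In the same edit, say what the two scenarios in the following sentence are, and check that the dispensing row of Table 4 and the Day 1 dispensing item agree with the reconciled text.

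The cost is one sentence, plus those consistency checks and the usual handling of a protocol clarification. No sample size, endpoint or analysis changes.
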